10.7. Appendix 7: Country-specific Requirements

The following lists modifications to the protocol's existing text that are required for specific countries. Cross-references to applicable sections of the protocol are included with each item.

10.7.1. China

PD and immunogenicity blood samples that are collected from participants in China may be used to develop and validate methods to support the efgartigimod development program. Such use of these samples is only permitted after obtaining approval from the HGRAC, and the methods in which they are used must comply with local regulations. Additionally, the conditions in which these samples are stored and ultimately destroyed must comply with HGRAC requirements and other relevant regulations (Section 8.6 and Section 8.9).

In China, oral methylprednisolone will be provided instead of oral prednisone (Section 6.9.1). Refer to Table 9 for the concurrent oral methylprednisolone dose regimen.

Table 9: Concurrent Oral Methylprednisolone Equivalent Doses (in mg) Based on Participant Body Weight

Oral prednisone dose level	Body weight category ^a (kg)															
	<45 kg	≥45 to <50	≥50 to <55	≥55 to <60	≥60 to <65	≥65 to <70	≥70 to <75	≥75 to <80	≥80 to <85	≥85 to <90	≥90 to <95	≥95 to <100	≥100 to <105	≥105 to <110	≥110	
	Minimum recommended daily methylprednisolone dose	Daily methylprednisolone dose ^b													Maximum recommended daily methylprednisolone dose	
mg/kg/day	mg/day															
1.0	32	36	40	44	48	52	56	60	64	68	72	76	80	84	88	
0.75	24	24	28	32	36	36	40	44	48	48	52	56	60	60	64	
0.50	16	18	20	20	24	24	28	28	32	32	36	36	40	40	48	
0.30	10	10	12	12	14	14	16	18	18	20	20	20	24	24	32	
0.20	6	6	8	8	8	10	10	12	12	12	14	14	16	16	20	
0.15	4	4	6	6	6	6	8	8	8	10	10	10	12	12	14	
Minimal OCS therapy: ≤0.10	2	2	4	4	4	4	4	6	6	6	6	6	8	8	10	
mg/day	mg/day															
7.5	NA	NA	NA	NA	NA	NA	NA	NA	NA	NA	NA	NA	NA	6	6	6
5.0	NA	NA	NA	NA	NA	NA	NA	4	4	4	4	4	4	4	4	
2.5	NA	NA	2	2	2	2	2	2	2	2	2	2	2	2	2	
Off OCS therapy: 0	0	0	0	0	0	0	0	0	0	0	0	0	0	0	0	

NA=not applicable; OCS=oral corticosteroids (oral methylprednisolone)

Notes: Each new dosage will be maintained for 2 weeks or less, based on the investigator’s clinical judgment.

^a Body weight should be rounded to the nearest whole number.

- ^b The investigator should not deviate from the concurrent oral methylprednisolone dose levels specified in the table, except if the participant's safety could be compromised.

CRoff	complete remission off OCS therapy
CTCAE	Common Terminology Criteria for Adverse Events
CTP	clinical trial protocol
CWS	cumulative worsening score
DBP	diastolic blood pressure
DLQI	dermatology life quality index
ECG	electrocardiogram
eCRF	electronic case report form
EDV	early discontinuation visit
EFG	efgartigimod
eGFR	estimated glomerular filtration rate
EoTP	end of treatment period

	Statistical Analysis Plan	
ARGX-113-2010	Final analysis	Final 1.0 of 29APR2025

EQ-5D-5L	EuroQoL 5 Dimensions 5 Levels
FU	follow-up
GM	geometric mean
GSD	geometric standard deviation
GTI	glucocorticoid toxicity index
GTI-SL	glucocorticoid toxicity index - specific list
HR	heart rate
ICF	informed consent form
ICH	International Council for Harmonization of Technical Requirements for Pharmaceuticals for Human Use
ID	identification
IGA-BP	investigator global assessment of bullous pemphigoid
█	█
IMP	investigational medicinal product
IRR	injection-related reaction
ISR	injection site reaction
MedDRA	Medical Dictionary for Regulatory Activities
NAb	neutralizing antibody
NA	not applicable
NCI	National Cancer Institute
OCS	oral corticosteroids
OLE	open-label extension
PAS	participant analysis set
PD	pharmacodynamic(s)
PI	principal investigator
PRO	patient-reported outcome
PT	preferred term
PYFU	patient years of follow-up
QoL	quality of life
QTc	corrected QT interval
QTcB	Bazett's corrected QT interval
QTcF	Fridericia's corrected QT interval
rHuPH20	recombinant human hyaluronidase PH20
ROL	rollover analysis set

	Statistical Analysis Plan	
ARGX-113-2010	Final analysis	Final 1.0 of 29APR2025

SAE	serious adverse event
SAF	safety analysis set
SAP	statistical analysis plan
SBP	systolic blood pressure
SC	subcutaneous(ly)
SDTM	study data tabulation model
SGS CR	SGS Clinical Research
SoA	schedule of activities
SoC	standard of care
SOC	system organ class
SOP	standard operating procedure
SMQ	Standardized MedDRA Queries
STAT	statistics
TCS	topical corticosteroids
TEAE	treatment-emergent adverse event
TLF	tables, listings, and figures
VS	vital signs
WHO	World Health Organization
WI	work instruction

	Statistical Analysis Plan	
ARGX-113-2010	Final analysis	Final 1.0 of 29APR2025

DEFINITION OF TERMS

CRF	A printed, optical, or electronic document designed to record protocol required information to be reported to the sponsor for each study participant.
Complete remission on minimal OCS therapy (CRmin)	Being in complete remission (CR) for ≥ 8 weeks and have been on minimal OCS therapy (≤ 0.10 mg/kg/day of prednisone or an equivalent dose of another OCS) for ≥ 8 weeks
Complete remission off OCS therapy (CROff)	Being in CR for ≥ 8 weeks and have been off OCS therapy for ≥ 8 weeks.
display	Analysis table, listing, or figure
IMP	Pharmaceutical form of an active ingredient or placebo, being tested or used as a reference in a clinical study.
missing data	Data that would be meaningful for the analysis of a given endpoint but were not collected. They should be distinguished from data that do not exist.
standardized unit	unit populating --STRESU in the clinical database
treatment-emergent abnormality / toxicity	
Any postbaseline* abnormality/toxicity which was not present at the study baseline or worsened after the study baseline (e.g., hemoglobin normal or grade 1 at baseline and grade 2 postbaseline; glucose low at baseline and high postbaseline; QTcF [450; 480] ms at baseline and >500 ms postbaseline). If baseline is missing, any postbaseline abnormality/toxicity will be considered emergent.
 
*Note: postbaseline records on or after the first administration of IMP in ARGX-113-2010 and up to and including 60 days after the last IMP administration before the assessment will be considered for treatment-emergence.

	Statistical Analysis Plan	
ARGX-113-2010	Final analysis	Final 1.0 of 29APR2025

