6.3. Assignment to Study Intervention

The following general principles apply to all participants. These principles apply to the specific situations described in Section 6.3.1 and Section 6.3.2 unless mentioned otherwise.

- Efgartigimod PH20 SC can be initiated until week 45 to ensure a minimum of 4 weeks of treatment.
- Efgartigimod PH20 SC should be initiated without concurrent OCS if the participant's BP disease status permits it, according to the investigator's clinical judgment.
- Localized lesions should be treated with TCS before concurrent OCS treatment is considered, if possible.
- If there is no improvement in the participant's BP disease status and additional BP therapy is required while receiving efgartigimod PH20 SC, concurrent OCS treatment may be initiated according to the investigator's clinical judgment. Recommendations for OCS therapy initiation and tapering are provided in Section 6.9.1.
- As described in Section 6.9.2, rescue therapy will be tapered or discontinued in participants who received it in ARGX-113-2009. IMP will be permanently discontinued if the investigator considers it not to be in the participant's best interest to taper or discontinue rescue therapy.

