2.2 PHASES, PERIODS AND TIME POINTS

2.2.1 *Analysis phases, periods and subperiods*

All assessments and events will be allocated to analysis phases, periods and subperiods as defined in below table.

Table 2: Analysis phase, period and subperiod definition

Phase	Period/Subperiod	Start	End
For participants who don't receive the first IMP administration at the ARGX-113-2010 baseline visit^a, the first phase will be the observation phase.			
For participants who receive the first IMP administration at the ARGX-113-2010 baseline visit^a, the first phase will be the treatment phase.			
Observation		Date of baseline visit in ARGX-113-2010, with 00:00 added as time part	
For participants with a subsequent treatment period:
 
First IMP administration date/time – 1 minute.
 
For other participants:
 
Date of week 48 or EDV visit^c, with 23:59 added as time part.
 
For participants who don't have a week 48 or EDV visit: date of last contact, with 23:59 added as time part.

	Statistical Analysis Plan	
ARGX-113-2010	Final analysis	Final 1.0 of 29APR2025

Phase	Period/Subperiod	Start	End
Treatment	Treatment period 1/ On IMP treatment	
For participants with first IMP administration at the baseline visit:
 
Date of baseline visit in ARGX-113-2010, with 00:00 added as time part.
 
For participants with a previous observation phase and who initiate treatment:
 
First IMP administration date/time
	
For participants with a subsequent Off IMP subperiod:
 
Last IMP administration date/time in treatment period 1.
 
For other participants:
 
Date of week 48 or EDV visit^c, with 23:59 added as time part.
 
For participants who don't have a week 48 or EDV visit: date of last contact, with 23:59 added as time part.

	Treatment period 1/ Off IMP treatment	Last IMP administration date/time in treatment period 1 + 1 minute	
For participants with a subsequent treatment period:
 
First IMP administration date/time in next treatment period – 1 minute.
 
For other participants:
 
Date of week 48 or EDV visit^c, with 23:59 added as time part.
 
For participants who don't have a week 48 or EDV visit: date of last contact, with 23:59 added as time part.

Treatment period 2 is applicable for participants who re-initiate IMP administration after a previous Off IMP subperiod^b.			

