Adverse events will be allocated to phases as described in section 5.1.2. Concomitant therapies and procedures will be allocated to phases and (sub)periods as described in section 3.3.2. All other assessments will be allocated to phases and (sub)periods based on the assessment date/time. In case of (partially) missing date/time fields disabling allocation of an assessment to phases or (sub)periods, information from the visit label, time point label and the protocol schedule of activities will be used to allocate to the correct phase.

For efficacy assessments without time part, an assessment on the day of switch from observation phase to treatment phase will be considered as part of the treatment phase. Likewise, an assessment on the day of switch from treatment period 1 to treatment period 2 will be considered as part of treatment period 2.

2.2.2 *Baseline and change from baseline*

Study baseline is defined as the first available and nonmissing value at the baseline visit (scheduled or unscheduled) in ARGX-113-2010. This value corresponds with the value at the EoTP visit in ARGX-113-2009 (and is copied over into the database of ARGX-113-2010 at SDTM level).

Change from baseline is defined as:

- Change from baseline at time point t = value at time point t – baseline value.

Percentage change from baseline at time point t is defined as follows:

- When baseline value is not zero: $100 * ((\text{value at time point } t - \text{baseline value}) / \text{baseline value})$
- When both baseline value and value at time point t are zero: 0
- When baseline value is zero and value at time point t is not zero: not calculated

For immunogenicity assessments, the study baseline selection will be performed by sample (not by parameter) in order to keep the ADA and NAb results of a sample together. Furthermore, values resulting in an unevaluable ADA status are given the lowest priority when the selection is made.

For evaluation of PD parameters, a treatment period-specific baseline (TPnB) will be defined:

	Statistical Analysis Plan	
ARGX-113-2010	Final analysis	Final 1.0 of 29APR2025

- For a treatment period, TPnB is the last available and non-missing value prior to the first IMP administration in the treatment period. Assessments on day 1 of a treatment period without time collection or with time information exactly equal to the time of first IMP administration and which are planned predose will be considered as predose.

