5.2.3 Presentation of results

The SAF analysis set will be used for the clinical laboratory evaluation. For tables by analysis visit, only the baseline and last assessment analysis visits will be shown. Cross-tabulations will also include the worst-case analysis visit. All other analysis visits will be included in listings.

Only continuous laboratory parameters expected per protocol will be tabulated, except for INR. The statistical analysis will present results in standardized units, except for creatinine clearance (adjusted for BSA), which will be reported in mL/min/1.73m².

Continuous laboratory parameters will be summarized using descriptive statistics at each analysis visit of interest. Actual values and changes from study baseline will be shown in the same table.

Laboratory abnormalities will be presented as cross-tabulations of the abnormality at each postbaseline analysis visit of interest versus the study baseline abnormality. The number of participants with treatment-emergent abnormalities will also be shown (see Definition of terms). The denominator for the percentage is the total number of

	Statistical Analysis Plan	
ARGX-113-2010	Final analysis	Final 1.0 of 29APR2025

participants with nonmissing data for the parameter and analysis visit in the SAF analysis set.

Laboratory toxicity grades will be presented as cross-tabulations of the toxicity at each postbaseline analysis visit of interest versus the study baseline toxicity. Numbers and cumulative numbers over decreasing toxicity grading of participants with treatment-emergent toxicities will also be shown. The denominator for the percentage is the total number of participants with nonmissing data for the parameter and analysis visit in the SAF analysis set. Parameters with toxicity grades defined in both directions (hypo and hyper) will be shown by direction.

All laboratory data will be listed for the ROL analysis set, including laboratory tests not foreseen per protocol, but only for participants with any postbaseline abnormality or toxicity grade ≥ 1 .

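### For participants first dosed after an observation phase, treatment-emergent laboratory and vital-sign abnormalities are judged against the rollover value, not the last value before the first dose

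*SAP*

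**What the plan says.** **Reference value.** The SAP's Definition of Terms counts as treatment-emergent an abnormality or toxicity "which was not present at the study baseline or worsened after the study baseline". SAP 2.2.2 fixes the reference: "Study baseline is defined as the first available and nonmissing value at the baseline visit (scheduled or unscheduled) in ARGX-113-2010". That value is carried over from the end-of-treatment visit of ARGX-113-2009.

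**Eligible records.** A note to the same definition limits which records count: "postbaseline records on or after the first administration of IMP in ARGX-113-2010 and up to and including 60 days after the last IMP administration". The 60 days run from the most recent dose preceding the record. SAP 2.2.5 limits the worst-case visit in the same way.

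**Displays.** SAP 5.2.3 cross-tabulates laboratory abnormalities "at each postbaseline analysis visit of interest versus the study baseline abnormality". SAP 5.3.3 and 5.4.3 do the same for vital signs and ECG.

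**Delayed first dose.** SAP Table 2 (section 2.2.1) opens with an observation phase "For participants who don't receive the first IMP administration at the ARGX-113-2010 baseline visit". Protocol 6.3 sets the outer limit: "Efgartigimod PH20 SC can be initiated until week 45 to ensure a minimum of 4 weeks of treatment".

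**The alternative reference.** SAP 2.2.2 also has a baseline reset at dosing: "TPnB is the last available and non-missing value prior to the first IMP administration in the treatment period". Its scope is narrow: "For evaluation of PD parameters, a treatment period-specific baseline (TPnB) will be defined".

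**The concern.** A treatment-emergent label should separate what appeared or worsened after dosing began from what was already there. For a participant dosed at rollover, the rollover value does that. For a participant with an observation phase, the reference and the first dose can be months apart, and no section of the SAP resets the reference for laboratory, vital-sign or ECG data.

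Two errors follow, in opposite directions. A change that arose untreated and persists past the first dose is counted as emergent. A change present at rollover that resolved off drug and recurs on drug is not counted, because it is no worse than rollover. The second deserves attention in a safety study. SAP 4.1.2 (endpoint 5) bars only former placebo participants from evaluation in the observation phase, which implies that former efgartigimod participants can enter there too. Their rollover value may therefore reflect drug exposure.

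The rule also disagrees with the SAP's own adverse-event rule. SAP 5.1.2 goes by onset, so an adverse event that began before the first dose and persisted is not treatment-emergent. The same finding held as a laboratory value is.

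**Working it through.** Neither document states a figure on this point, so there is nothing to reproduce. The check has three steps.

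**1. Apply the rule to constructed cases.** Inputs: first dose on day 113 (7 × 16 + 1, week 16), last dose on day 330, and toxicity grades at five records. A record is eligible from day 113 up to 60 days after the last dose (Definition of Terms). It is emergent if its grade exceeds the reference grade.

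| Case | Grade on days 1 / 57 / 112 / 127 / 141 | Reference: rollover (day 1) | Reference: last pre-dose (day 112) |
|---|---|---|---|
| A. Transient, gone before dosing | 0 / 2 / 0 / 0 / 0 | not emergent | not emergent |
| B. Arises untreated, persists | 0 / 2 / 2 / 2 / 2 | **emergent** | not emergent |
| C. Arises untreated, improves on drug | 0 / 3 / 3 / 2 / 1 | **emergent** | not emergent |
| D. At rollover, resolves, recurs on drug | 2 / 0 / 0 / 2 / 2 | not emergent | **emergent** |
| E. New on drug | 0 / 0 / 0 / 2 / 2 | emergent | emergent |

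The references disagree in B, C and D. In C, an abnormality that improves on drug is still labelled emergent. A and E come out the same either way.

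**2. How old the reference can be, and what else is available.** The longest gap is 45 × 7 = 315 days. Protocol Table 1 schedules chemistry, hematology and vital signs at weeks 2, 4, 8, 16, 24, 32 and 40, so up to seven later pre-dose visits can exist. Protocol Table 2 adds these measurements on day X, and Protocol 8.3 places them before dosing. ECG is different: Table 1 has ECGs only at baseline and week 24, and Table 2 has none on day X. Apart from unscheduled ECGs, a later pre-dose ECG exists only if dosing starts at or after about week 24.

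**3. Size of the overcount (cases B and C).** In percentage points:

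overcount = 100 × f × q × r

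- f: share of the safety set that starts late, assumed 5% to 30%
- q: share of those with a new abnormality of the parameter while untreated, assumed 5% to 30%
- r: share of those still abnormal at an eligible record, assumed 50% to 100%

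| Scenario | f × q × r | Overcount (points) |
|---|---|---|
| Low | 0.05 × 0.05 × 0.5 | 0.125 |
| Middle | 0.15 × 0.10 × 1.0 | 1.5 |
| High | 0.30 × 0.30 × 1.0 | 9.0 |

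None of these inputs is in the documents. The formula covers overcounting only. Case D pulls the other way, so this is not a net bias.

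**A related gap.** SAP 5.3.1 lists a date but no time for vital signs, and the rule in SAP 2.2.1 for untimed records on a switch day covers efficacy only. An untimed vital sign taken before dosing on day X could thus be read as on or after the first dose.

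**The case against.** The strongest defence has four parts.

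- **The record window already protects the label.** A reader might infer that abnormalities seen before dosing are generally attributed to the drug. The documents do not support that. The note to the definition and SAP 2.2.5 exclude anything recorded only before the first dose (case A). The label also concerns timing; relatedness is judged by the investigator, for adverse events. This stands and narrows the point to changes that persist or recur.
- **The primary endpoints are untouched.** A reader might infer that the primary safety result is biased. The primary endpoints are treatment-emergent adverse events, serious events, events of special interest, and discontinuation for safety. Adverse events follow the onset rule, and clinically significant laboratory or ECG findings are reported as adverse events. This stands too.
- **The choice follows the protocol.** Protocol 9.3.1 sets baseline at the antecedent study's end-of-treatment value, and the listings, ordered by phase and visit, would show onset during observation. That is true, but the same protocol section lets the SAP use another baseline for specific analyses (it names the ARGX-113-2009 baseline), and a listing does not correct a count in a table.
- **Few may be affected.** From amendment 2, participants are generally dosed at rollover, with exceptions such as temporary interruption (Protocol 5.5), and participants never dosed are outside the safety set. That limits the size but does not remove the misclassification.

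A reader might also want the reference reset for treatment period 2. That does not follow. SAP 2.2.1 lets a new period begin after a 28-day gap, while records stay eligible for 60 days after the last dose. A pre-period-2 value taken between days 28 and 60 can itself be treatment-emergent, so it is not a clean reference.

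**Conclusion.** The point holds for participants who enter in the observation phase, are dosed later, and change status in between. For them the rollover reference overcounts untreated abnormalities that persist and misses those that cleared and came back on drug. It matters for laboratory and vital-sign tables, and for ECG only where a later pre-dose ECG exists. These are supportive descriptive tables with no hypothesis test.

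The size is unknown, because neither document gives the number of delayed starters or how often their status changes. The 0.1 to 9 points per parameter, with 1.5 in the middle scenario, rests wholly on the assumed inputs and covers one direction only. The classification result in the five cases needs no such assumption; it follows from the SAP text. The change is worth making because the SAP already contains a suitable rule and the cost is low.

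**What to change.** In the Definition of Terms, and in the emergence counts and worst-case cross-tabulations of SAP 5.2.3, 5.3.3 and 5.4.3, take as reference the last non-missing value before the first dose of IMP in ARGX-113-2010.

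- Extend to these data the SAP 2.2.2 convention under which day 1 records without a time, but planned before dosing, count as predose. This also closes the vital-sign timing gap.
- Where no later pre-dose value exists, as often for ECG, the reference remains the rollover value.
- Keep this single reference for both treatment periods; do not switch to the period 2 baseline.
- Keep study baseline for the change-from-baseline tables and for one supportive shift table.
- Report the number of delayed starters in the safety set beside the tables, so that the reach of the rule is visible.

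Results for participants dosed at rollover do not change, unless a repeat value at an unscheduled baseline visit precedes the dose. The cost is SAP wording, minor programming to extend a derivation now defined only for PD, and one additional supportive table. No new data collection is needed.

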1. INTRODUCTION

This SAP describes the statistical analyses to be performed for the final analysis of study ARGX-113-2010 (BE-80-2200433). It is based on the most recent version of the protocol, version 4.0 of 02 May 2024. Table, figure and listing specifications will follow the argenx generic mock TLF library, unless mentioned otherwise.

This SAP describes the safety, efficacy, pharmacodynamics (PD), immunogenicity and general characteristics sections of the statistical analysis. It specifies the analysis displays to be presented and elaborates on the methods and procedures described in the statistical methods section of the protocol.

The statistical analysis will process and present the results following the ICH standards, in particular the ICH-E3, ICH-E6, and ICH-E9 guidelines.

